10.4. Appendix 4: Contraceptive and Barrier Guidance

10.4.1. Male Participant Reproductive Inclusion Criteria

Male participants are eligible to participate if they agree to the following requirements during the intervention period and for at least 30 days after the last dose of study intervention, which corresponds to the time needed to eliminate reproductive safety risk of the study intervention(s) **plus** an additional 90 days (a spermatogenesis cycle):

- Refrain from donating sperm.

PLUS either:

- Be abstinent from heterosexual intercourse as their preferred and usual lifestyle (abstinent on a long-term and persistent basis) and agree to remain abstinent;

OR

- Must agree to use contraception/barrier as detailed below:
 - Agree to use a male condom when engaging in any activity that allows for passage of ejaculate to another person.
 - Use of an additional highly effective contraceptive method with a failure rate of <1% per year as described below in [Section 10.4.4](#) for a female partner of childbearing potential.

10.4.2. Female Participant Reproductive Inclusion Criteria

Females are not eligible to enroll in this study

10.4.3. Woman of Childbearing Potential

A woman is considered fertile following menarche and until becoming postmenopausal unless permanently sterile (see below).

If fertility is unclear (eg, amenorrhea in adolescents or athletes) and a menstrual cycle cannot be confirmed before the first dose of study intervention, additional evaluation should be considered.

Women in the following categories are not considered WOCBP:

1. Premenarchal.
2. Premenopausal female with 1 of the following:
 - Documented hysterectomy;

- Documented bilateral salpingectomy;
- Documented bilateral oophorectomy.

For individuals with permanent infertility due to an alternate medical cause other than the above, (eg, mullerian agenesis, androgen insensitivity), investigator discretion should be applied to determining study entry.

Note: Documentation for any of the above categories can come from the site personnel's review of the participant's medical records, medical examination, or medical history interview. The method of documentation should be recorded in the participant's medical record for the study.

3. Postmenopausal female.

- A postmenopausal state is defined as no menses for 12 months without an alternative medical cause. In addition:
 - A high FSH level in the postmenopausal range must be used to confirm a postmenopausal state in women under 60 years old and not using hormonal contraception or HRT.
 - A female on HRT and whose menopausal status is in doubt will be required to use one of the nonestrogen hormonal highly effective contraception methods if they wish to continue their HRT during the study. Otherwise, they must discontinue HRT to allow confirmation of postmenopausal status before study enrollment.

10.4.4. Contraception Methods

Contraceptive use by men or women should be consistent with local availability/regulations regarding the use of contraceptive methods for those participating in clinical trials.

Highly Effective Methods That Have Low User Dependency

1. Implantable progestogen-only hormone contraception associated with inhibition of ovulation.
2. Intrauterine device.
3. Intrauterine hormone-releasing system.
4. Bilateral tubal occlusion (eg, bilateral tubal ligation).

5. Vasectomized partner.

- A vasectomized partner is a highly effective contraceptive method provided that the partner is the sole sexual partner of the WOCBP and the absence of sperm has been confirmed. If not, an additional highly effective method of contraception should be used. The spermatogenesis cycle is approximately 90 days.

Highly Effective Methods That Are User Dependent

6. Combined (estrogen- and progestogen-containing) hormonal contraception associated with inhibition of ovulation.
 - Oral;
 - Intravaginal;
 - Transdermal;
7. Progestogen-only hormone contraception associated with inhibition of ovulation.
 - Oral;
 - Injectable.
8. Sexual abstinence.
 - Sexual abstinence is considered a highly effective method only if defined as refraining from heterosexual intercourse during the entire period of risk associated with the study intervention. The reliability of sexual abstinence needs to be evaluated in relation to the duration of the study and the preferred and usual lifestyle of the participant.

One of the following effective barrier methods must be used in addition to the highly effective methods listed above that are user dependent:

- Male or female condom with or without spermicide;
- Cervical cap, diaphragm, or sponge with spermicide;
- A combination of male condom with either cervical cap, diaphragm, or sponge with spermicide (double-barrier methods).

10.5. Appendix 5: Genetics

Genetics (specified analyses) are not evaluated in this study.

10.6. Appendix 6: Liver Safety: Suggested Actions and Follow-Up Assessments

Potential Cases of Drug-Induced Liver Injury

Humans exposed to a drug who show no sign of liver injury (as determined by elevations in transaminases) are termed “tolerators,” while those who show transient liver injury but adapt are termed “adaptors.” In some participants, transaminase elevations are a harbinger of a more serious potential outcome. These participants fail to adapt and therefore are “susceptible” to progressive and serious liver injury, commonly referred to as DILI. Participants who experience a transaminase elevation above $3 \times$ ULN should be monitored more frequently to determine if they are “adaptors” or are “susceptible.”

LFTs are not required as a routine safety monitoring procedure in this study. However, should an investigator deem it necessary to assess LFTs because a participant presents with clinical signs/symptoms, such LFT results should be managed and followed as described below.

In the majority of DILI cases, elevations in AST and/or ALT precede TBili elevations ($>2 \times$ ULN) by several days or weeks. The increase in TBili typically occurs while AST/ALT is/are still elevated above $3 \times$ ULN (ie, AST/ALT and TBili values will be elevated within the same laboratory sample). In rare instances, by the time TBili elevations are detected, AST/ALT values might have decreased. This occurrence is still regarded as a potential DILI. Therefore, abnormal elevations in either AST OR ALT in addition to TBili that meet the criteria outlined below are considered potential DILI (assessed per Hy’s law criteria) cases and should always be considered important medical events, even before all other possible causes of liver injury have been excluded.

The threshold of laboratory abnormalities for a potential DILI case depends on the participant’s individual baseline values and underlying conditions. Participants who present with the following laboratory abnormalities should be evaluated further as potential DILI (Hy’s law) cases to definitively determine the etiology of the abnormal laboratory values:

- Participants with AST/ALT and TBili baseline values within the normal range who subsequently present with AST OR ALT values $>3 \times$ ULN AND a TBili value $>2 \times$ ULN with no evidence of hemolysis and an alkaline phosphatase value $<2 \times$ ULN or not available.
- For participants with baseline AST **OR** ALT **OR** TBili values above the ULN, the following threshold values are used in the definition mentioned above, as needed, depending on which values are above the ULN at baseline:
 - Preexisting AST or ALT baseline values above the normal range: AST or ALT values >2 times the baseline values AND $>3 \times$ ULN; or $>8 \times$ ULN (whichever is smaller).

- Preexisting values of TBili above the normal range: TBili level increased from baseline value by an amount of at least $1 \times \text{ULN}$ **or** if the value reaches $>3 \times \text{ULN}$ (whichever is smaller).

Rises in AST/ALT and TBili separated by more than a few weeks should be assessed individually based on clinical judgment; any case where uncertainty remains as to whether it represents a potential Hy's law case should be reviewed with the sponsor.

The participant should return to the investigator site and be evaluated as soon as possible, preferably within 48 hours from awareness of the abnormal results. This evaluation should include laboratory tests, detailed history, and physical assessment.

In addition to repeating measurements of AST and ALT and TBili for suspected Hy's law cases, additional laboratory tests should include albumin, CK, direct and indirect bilirubin, GGT, PT/INR, total bile acids, and alkaline phosphatase. Consideration should also be given to drawing a separate tube of clotted blood and an anticoagulated tube of blood for further testing, as needed, for further contemporaneous analyses at the time of the recognized initial abnormalities to determine etiology. A detailed history, including relevant information, such as review of ethanol, acetaminophen/paracetamol (either by itself or as a coformulated product in prescription or over-the-counter medications), recreational drug, or supplement (herbal) use and consumption, family history, sexual history, travel history, history of contact with a jaundiced person, surgery, blood transfusion, history of liver or allergic disease, and potential occupational exposure to chemicals, should be collected. Further testing for acute hepatitis A, B, C, D, and E infection, liver imaging (eg, biliary tract), and collection of serum samples for acetaminophen/paracetamol drug and/or protein adduct levels may be warranted.

All cases demonstrated on repeat testing as meeting the laboratory criteria of AST/ALT and TBili elevation defined above should be considered potential DILI (Hy's law) cases if no other reason for the LFT abnormalities has yet been found. **Such potential DILI (Hy's law) cases are to be reported as SAEs, irrespective of availability of all the results of the investigations performed to determine etiology of the LFT abnormalities.**

A potential DILI (Hy's law) case becomes a confirmed case only after all results of reasonable investigations have been received and have excluded an alternative etiology.

10.7. Appendix 7: ECG Findings of Potential Clinical Concern

ECG Findings That May Qualify as AEs

• Marked sinus bradycardia (rate <40 bpm) lasting minutes.• New PR interval prolongation >280 msec.• New prolongation of QTcF to >480 msec (absolute) or by \geq60 msec from baseline.• New-onset atrial flutter or fibrillation, with controlled ventricular response rate: ie, rate <120 bpm.• New-onset type I second-degree (Wenckebach) AV block of >30 seconds' duration.• Frequent PVCs, triplets, or short intervals (<30 seconds) of consecutive ventricular complexes.
ECG Findings That May Qualify as SAEs

• QTcF prolongation >500 msec.• New ST-T changes suggestive of myocardial ischemia.• New-onset left bundle branch block (QRS >120 msec).• New-onset right bundle branch block (QRS >120 msec).• Symptomatic bradycardia.• Asystole:
• In awake, symptom-free participants in sinus rhythm, with documented periods of asystole \geq3.0 seconds or any escape rate <40 bpm, or with an escape rhythm that is below the AV node.• In awake, symptom-free participants with atrial fibrillation and bradycardia with 1 or more pauses of at least 5 seconds or longer.• Atrial flutter or fibrillation, with rapid ventricular response rate: rapid = rate >120 bpm.• Sustained supraventricular tachycardia (rate >120 bpm) ("sustained" = short duration with relevant symptoms or lasting >1 minute).• Ventricular rhythms >30 seconds' duration, including idioventricular rhythm (heart rate <40 bpm), accelerated idioventricular rhythm (HR >40 bpm to <100 bpm), and

monomorphic/polymorphic ventricular tachycardia (HR >100 bpm (such as torsades de pointes)).

- Type II second-degree (Mobitz II) AV block.
- Complete (third-degree) heart block.

ECG Findings That Qualify as SAEs

- Change in pattern suggestive of new myocardial infarction.
- Sustained ventricular tachyarrhythmias (>30 seconds' duration).
- Second- or third-degree AV block requiring pacemaker placement.
- Asystolic pauses requiring pacemaker placement.
- Atrial flutter or fibrillation with rapid ventricular response requiring cardioversion.
- Ventricular fibrillation/flutter.
- At the discretion of the investigator, any arrhythmia classified as an adverse experience.

The enumerated list of major events of potential clinical concern are recommended as “alerts” or notifications from the core ECG laboratory to the investigator and Pfizer study team, and not to be considered as all inclusive of what to be reported as AEs/SAEs.

10.8. Appendix 8: Prohibited Concomitant Medications That May Result in DDI

Concomitant medications are not allowed in this study

10.9. Appendix 9: Abbreviations

The following is a list of abbreviations that may be used in the protocol.

Abbreviation	Term
6MWT	six minute walk time distance
Abs	absolute
ADE	adverse device effect
ADL	activities of daily living
ADME	absorption, distribution, metabolism, excretion
AE	adverse event
AESI	adverse events of special interest
ALARA	as low as reasonably achievable
ALT	alanine aminotransferase
API	active pharmaceutical ingredient
AST	aspartate aminotransferase
AUC	area under the curve
AUC _{inf}	area under the concentration-time curve from time zero to infinity
AUC _{last}	area under the concentration -time curve from zero to time of last measurable concentration
AV	atrioventricular
BA	bioavailability
BBS	Biospecimen Banking System
BE	bioequivalence
BID	twice-a-day
BMI	body mass index
BP	blood pressure
bpm	beats per minute
BUN	blood urea nitrogen
CFR	Code of Federal Regulations
CIOMS	Council for International Organizations of Medical Sciences
CK	creatine kinase
C _{last}	last observable concentration
CL/F	Apparent clearance of drug from e.g.,plasma, for extravascular routes of administration
C _{max}	maximum observed concentration
CO ₂	carbon dioxide (bicarbonate)
COVID-19	coronavirus disease 2019
CRF	case report form
CRO	contract research organization

Abbreviation	Term
CRP	c-reactive protein
CRU	clinical research unit
CRU	clinical research unit
CSR	Clinical Study Report
CT	clinical trial; computed tomography
CYP	cytochrome P450
DDI	drug-drug interaction
DILI	drug-induced liver injury
DMC	Data Monitoring Committee
DMD	Duchenne muscular dystrophy
DNA	deoxyribonucleic acid
DU	dispensable unit
EC	ethics committee
ECC	emergency contact card
ECG	electrocardiogram
eCRF	electronic case report form
EDB	exposure during breastfeeding
EDMD	Emery-Dreifuss Muscular Dystrophy
EDP	exposure during pregnancy
EDR	extemporaneous dispensing record
EMA	European Medicines Agency
EU	European Union
EudraCT	European Clinical Trials Database
FDA	Food and Drug Administration
FMO	flavin monooxygenase
FSH	follicle-stimulating hormone
GCP	Good Clinical Practice
GGT	gamma-glutamyl transferase
GI	gastrointestinal
GMP	Good Manufacturing Practice
HBsAg	hepatitis B surface antigen
HCVAb	hepatitis C antibody
HIV	human immunodeficiency virus
HR	heart rate
HRT	hormone replacement therapy
HSP28	heat shock protein 28
IB	Investigator's Brochure
IBS	irritable bowel syndrome
IC ₅₀	concentration corresponding to 50% inhibition
ICD	informed consent document
ICH	International Council for Harmonisation of Technical Requirements

Abbreviation	Term
	for Pharmaceuticals for Human Use
ID	identification
ICRP	International Commission on Radiological Protection
IND	Investigational New Drug
INR	international normalized ratio
IOC	independent oversight committee
IP manual	investigational product manual
IPAL	Investigational Product Accountability Log
IRB	Institutional Review Board
IV	intravenous
K_{el}	Rate constant for terminal phase
LBBB	left bundle branch block
LFT	liver function test
Log_e	natural logarithm
LVEF	left ventricular ejection fraction
MAPK	mitogen-activated protein kinase
MCH	mean corpuscular hemoglobin
MCHC	mean corpuscular hemoglobin concentration
MCV	mean corpuscular volume
msec	millisecond
N/A	not applicable
NT-proBNP	N-terminal pro b-type natriuretic peptide
p38 α MAPK	p38-alpha mitogen activated protein kinase
PCR	polymerase chain reaction
PD	pharmacodynamic(s)
P-gp	P-glycoprotein
PI	principal investigator
PK	pharmacokinetic(s)
PO	oral
PT	prothrombin time
PVC	premature ventricular contraction/complex
QD	once daily
QTc	corrected QT
QTcF	corrected QT (Fridericia method)
QTL	quality tolerance limit
qual	qualitative
RNA	ribonucleic acid
RV	right ventricular
SADE	serious adverse device effect
SAE	serious adverse event
SAP	Statistical Analysis Plan

Abbreviation	Term
SARS-CoV-2	severe acute respiratory syndrome coronavirus 2
SCr	serum creatinine
SoA	schedule of activities
SOP	standard operating procedure
SRSD	single reference safety document
SUSAR	suspected unexpected serious adverse reaction
TBili	total bilirubin
THC	tetrahydrocannabinol
T _{max}	time of maximum observed concentration
t _{1/2}	terminal elimination half-life
TOC	table of contents
ULN	upper limit of normal
US	United States
USADE	unanticipated serious adverse device effect
V _{z/F}	Apparent volume of distribution, estimated from terminal phase, for extravascular dosing
WBC	white blood cell
WOCBP	woman/women of childbearing potential

1. AMENDMENTS FROM PREVIOUS VERSION(S)

None.

2. INTRODUCTION

PF-07265803 (formerly known as known as ARRY-371797) is a potent and selective, oral small molecule inhibitor of the α isoform of p38 MAPK. Mutations in the LMNA gene encoding nuclear lamina components cause nuclear envelope dysfunction leading to altered nuclear activity, impaired structural dynamics and aberrant cell signaling including activation of p38 α MAPK signaling pathways. Structural alterations in the nuclear envelope and connected cytoskeleton resulting from LMNA mutations make cardiomyocytes highly susceptible to damage even by physiological mechanical stress, leading to a disease specific maladaptive activation of the p38 α MAPK. Up-regulation of p38 MAPK has been observed in the hearts of animal models and adult patients with LMNA-related DCM compared to wild-type/healthy individuals. Inhibition of p38 MAPK in this disease setting may halt aberrant apoptosis and cardiac remodeling resulting in improved cardiac function.

2.1. Study Design

This is a Phase 1, open-label, single-period, single-center, non-randomized single oral dose study administering a liquid formulation with 400 mg of PF-07265803 containing 100 μ Ci of [14 C]PF-07265803 to healthy male participants. Participants will be screened for participation in this study within 28 days before dosing on Day 1 to confirm that they meet the inclusion/exclusion criteria specified in protocol Section 5.1.

The duration of this non-randomized Phase 1, open-label, single-center, single-dose study is approximately 7 days, with a 30-day safety follow up. The maximum period of confinement is expected to be 14 days. The minimum period of confinement is expected to be 3 days. Inpatient stay must be extended until >90% radioactive dose administered has been recovered or <1% is excreted in total (urine and feces) in any 24H period for two consecutive days. Maximum confinement will be 14 days.

The expected duration of participation from Screening to the follow-up telephone contact will be approximately 5 weeks (minimum) to 8 weeks (maximum). Approximately 6 participants will be enrolled to study intervention.

On Day-1, participants will be admitted in order to ensure that a group of 6 participants are dosed on Day 1. The study will dose 6 adult male participants in order to ensure that at least 4 participants provide evaluable data. There are no plans to replace participants who are prematurely withdrawn.

2.2. Study Objectives

2.2.1. Primary Objectives

- *To characterize rate and extent of excretion of total radioactivity in urine and feces, following a single oral dose of [¹⁴C]PF-07265803 administered to healthy adult male participants.*
- *To characterize metabolic profile and identify circulating and excreted metabolites following administration of a single oral dose of [¹⁴C]PF-07265803 to healthy adult male participants.*

2.2.2. Secondary Objective

- *To quantify plasma concentrations and pharmacokinetic parameters of PF-07265803, its known circulating metabolites (PF-07327859, PF-07327860, PF-07327890) and total radioactivity in plasma following administration of a single oral dose of [¹⁴C]PF-07265803 to healthy adult male participants.*
- *To evaluate safety and tolerability of a single oral dose of [¹⁴C]PF-07265803 administered to healthy adult male participants.*

3. INTERIM ANALYSES, FINAL ANALYSES AND UNBLINDING

No formal interim analysis will be conducted for this study. As this is an open-label study, the sponsor may conduct unblinded reviews of the data during the course of the study for the purpose of safety assessment, facilitating PK/PD modeling, and/or supporting clinical development.

4. HYPOTHESES AND DECISION RULES

4.1. Statistical Hypotheses

No hypotheses are required.

4.2. Statistical Decision Rules

No decision rules are required.

5. ANALYSIS SETS

5.1. Pharmacokinetic (PK) Analysis Set

5.1.1. PK Concentration Analysis Set

The PK concentration population for PF-07265803 is defined as all participants who receive at least 1 dose of PF-07265803 and who have at least 1 measurable concentration of PF-07265803 (Or its known circulating metabolites PF-07327859, PF-07327860, PF-07327890). The PK concentration population for ¹⁴C is defined as all participants dosed with [¹⁴C]PF-07265803, who have at least one ¹⁴C measurement.

5.1.2. PK Parameter Analysis Set

The PK parameter analysis population for PF-07265803 is defined as all participants treated who have at least 1 of the PF-07265803 (Or its known circulating metabolites PF-07327859, PF-07327860, PF-07327890) PK parameters of interest. The PK parameter analysis population for ¹⁴C analysis is defined as all participants treated who have at least one of the ¹⁴C parameters of interest. The PK concentration and PK parameter analysis sets may differ.

5.1.3. Extent of Excretion Analysis Set

Extent of excretion population is defined as all participants who have received 1 dose of [¹⁴C]PF-07265803 and who have evaluable total radioactivity concentration (urinary and fecal) data and who had no protocol deviations or AEs (such as vomiting of the dose, diarrhoea or severe constipation) that may have affected the extent of excretion analysis.

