8.4.3.5. Emesis Sample Collection for Total Radioactivity

If emesis occurs within the first 24 hours post dosing, vomitus will be collected for potential analysis of radioactivity. Approximately 4 mL should be collected if emesis occurs. All emesis discharge including any swabbing, contaminated linens and facial tissues used to collect bodily discharge (eg, nose bleeding clean-up tissue and any emesis related clean-up) should be collected and stored in a labeled emesis bag at minimally -20°C for possible analysis of radioactivity. Detailed sample handling instructions will be provided separately to the site before the start of the study.

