5.6.2. Deviations Assessed Post-Randomization

A full list of protocol deviations for the study report will be compiled prior to database closure. Any significant deviation from the protocol will be reviewed prior to database closure and a decision taken regarding evaluation for each analysis population.

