7.3. Pharmacokinetic Parameters

Actual PK sampling times will be used in the derivation of PK parameters.

If a PK parameter cannot be derived from a subject’s concentration data, the parameter will be coded as NC (ie, not calculated). (Note that NC values will not be generated beyond the day that a subject discontinues).

In summary tables, statistics will be calculated by setting NC values to missing; and statistics will be presented for a particular group with ≥ 3 evaluable measurements.

If an individual subject has a known biased estimate of a PK parameter (due for example to an unexpected event such as vomiting before all the compound is adequately absorbed in the body), this will be footnoted in summary tables and will not be included in the calculation of summary statistics or statistical analyses.

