8.2. Statistical Analyses

8.2.1. Pharmacokinetic Analysis

The PK parameters detailed in [Section 6.3](#) will be listed and summarized for subjects in the appropriate analysis sets (as defined in [Section 5.1.2](#)). Missing values will be handled as detailed in [Section 7](#).

PK parameters will be summarized as specified in the table below. All parameters will be presented in the same table using separate columns for plasma PK, plasma radioactivity.

Table 2. PK Parameters to be Summarized Descriptively

Parameter	Summary Statistics
AUC _{last} , AUC _{inf} , C _{max} , CL/F* and V _Z /F*	N, arithmetic mean, median, cv%, standard deviation, minimum, maximum, geometric mean and geometric cv%.
T _{max}	N, median, minimum, maximum.
t _{1/2}	N, arithmetic mean, median, cv%, standard deviation, minimum, maximum.

- For PF-07265803 only.

Box and whisker plots for individual subject parameters (AUC_{inf}, AUC_{last} and C_{max}) be presented and overlaid with geometric means.

Supporting data from the estimation of t_{1/2} and AUC_{inf} will be listed: terminal phase rate constant (k_{el}); goodness of fit statistic from the log-linear regression (r²); the percent of AUC_{inf} based on extrapolation (AUC_{extrap} %); and the first, last, and number of time points used in the estimation of k_{el}. This data may be included in the clinical study report.

Presentations for PK and total radioactivity (plasma) concentrations will include:

- A listing of all concentrations sorted by subject id and nominal time postdose. The listing of concentrations will include the actual times. Deviations from the nominal time will be given in a separate listing.
- A summary of concentrations by nominal time postdose, where the set of statistics will include n, mean, median, standard deviation, coefficient of variation (cv) and the number of concentrations above the lower limit of quantification.
- A plot of median PK and radioactivity concentrations against nominal time postdose (based on the summary of concentrations by time postdose), where the median concentration-time profiles for plasma PK, and plasma radioactivity will be presented together on the same plot.
- A log-linear plot of the median concentrations against nominal times postdose, as described above.
- Plots of individual concentrations against actual time postdose, where profiles for plasma PK, and plasma radioactivity, will be presented together on the same plot.

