8.2.2. Mass Balance

Radioactivity excreted in urine and/or feces will be reported as the percentage of the administered radioactivity excreted at each time interval, cumulatively through that interval and the total percent of dose recovered in urine and/or feces.

Percent recovery and cumulative recovery of total radioactivity in urine, feces and emesis (if any) will be determined based on total administered dose.

Individual participant and median data profiles will be graphically presented for the cumulative recovery of radioactivity in urine, feces and their combination. The total recovery of radioactivity in urine, feces and their combination will be listed and summarized using descriptive statistics. Where possible, the rate of excretion of radioactivity will be estimated.

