8.3.1. Treatment and Disposition of Subjects

Subject evaluation groups will show end of study subject disposition and will show which subjects were analyzed for pharmacokinetics, as well as for safety (adverse events and laboratory data). Frequency counts will be supplied for subject discontinuation(s).

Data will be reported in accordance with the sponsor reporting standards.

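### Does the primary mass-balance summary need a named analysis set and a written procedure for adverse-event exclusions?

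*SAP*

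**What the plan says.** SAP 5.1.3 and Protocol 9.2 (Table 2) define the Extent of Excretion set in the same terms. It takes participants who received the labelled dose, have evaluable urinary and fecal radioactivity, and had "no protocol deviations or AEs (such as vomiting of the dose, diarrhoea or severe constipation) that may have affected the extent of excretion" analysis.

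SAP 8.2.2 and Protocol 9.3.2 describe the primary analysis. On matrices: "Percent recovery and cumulative recovery of total radioactivity in urine, feces and emesis (if any) will be determined based on total administered dose". On the summary: "The total recovery of radioactivity in urine, feces and their combination will be listed and summarized using descriptive statistics". Individual and median cumulative profiles are also planned. Neither section cites an analysis set, whereas SAP 8.2.1 says that PK parameters "will be listed and summarized for subjects in the appropriate analysis sets" and points to 5.1.2.

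Protocol 8.4.3.5 covers vomitus: "If emesis occurs within the first 24 hours post dosing, vomitus will be collected for potential analysis of radioactivity".

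Three SAP sections deal with exclusions or their display:

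- 5.6.2: "Any significant deviation from the protocol will be reviewed prior to database closure and a decision taken regarding evaluation for each analysis population".
- 7.3, for a biased PK parameter: "this will be footnoted in summary tables and will not be included in the calculation of summary statistics".
- 8.3.1, where the evaluation groups "will show which subjects were analyzed for pharmacokinetics, as well as for safety (adverse events and laboratory data").

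**The concern.** Mass balance is a primary endpoint, yet its analysis section is silent on the population while the PK-parameter and safety sections are not. The emesis sentence adds doubt. If recovery in vomitus is to be determined, the analysis seems to expect participants who vomited, but the set that appears to apply gives vomiting of the dose as its first ground for leaving someone out.

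The exclusion also turns on whether an event may have affected the result. No criterion, time or responsible role is given for judging adverse events, and the review in SAP 5.6.2 is written for protocol deviations. The footnote rule in 7.3 concerns PK parameters, and the display in 8.3.1 does not mention excretion by name.

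With six participants and no replacement, one discretionary exclusion is a sixth of the data. It would be made after running recovery is known, because discharge depends on it. Diarrhea and nausea are among the commonest events reported in healthy subjects (Protocol 2.2.5), so the case is foreseeable. At stake would be a primary summary that could be run on either of two populations, with no record of who was dropped.

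**Working it through.** The documents give no exclusion rate, and the sample size of 6 has no formula behind it (Protocol 9.5), so there is no planned figure to reproduce. The check is mainly a comparison of passages, with one assumed example for size.

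**Which set.** Protocol 9.2 lists Enrolled, Safety, PK Concentration, PK Parameter and Extent of Excretion. Only the last requires urinary and fecal radioactivity, and its definition refers to the extent-of-excretion analysis. The first primary objective (SAP 2.2.1) concerns the rate and extent of excretion, and 8.2.2 is the only section that analyzes it. No other use for the set exists. The missing pointer is not peculiar to 8.2.2 either: within 8.2.1 the concentration summaries and plots cite no set, and the reader matches them by name.

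**Emesis.** The set does not exclude all vomiting, only events that may have affected the analysis. The protocol collects any vomitus in the first 24 hours, for potential measurement. The radioactivity found there is natural evidence for deciding whether dose was lost, so collection and exclusion work together. The summarized total covers urine, feces and the two combined, and the endpoint in SAP 6.3.2 is urinary, fecal and total excretion. Emesis therefore stands beside the total and not inside it.

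**Who decides, and when.** SAP 5.6.2 already sets a decision for every analysis population before database closure. It names deviations only, but set membership must be settled before the tables are run, and adverse events are reviewed throughout the study (SAP 8.3). Analysts would take the events to the same review.

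**Reporting.** The set is numbered 5.1.3, under the heading for PK analysis sets in 5.1, so the display of who was analyzed for pharmacokinetics can be read to include it. SAP 8.3.1 also defers to sponsor reporting standards that are not in these documents, so an omission cannot be shown. A participant absent from a listing and profiles of six would be noticed.

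**Size.** Share removed: 1/6 = 16.7% for one participant, and 2/6 = 33.3% for two, the most that leaves the planned minimum of 4. Assume five participants at 92% recovery and one with 60% in urine plus feces and 30% in vomitus:

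| Handling of the sixth participant | Mean | Median |
|---|---|---|
| Left out | 460/5 = 92.0% | 92% |
| Kept, urine plus feces | (460 + 60)/6 = 86.7% | 92% |
| Kept, vomitus added | (460 + 90)/6 = 91.7% | 92% |

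The largest difference in the mean is 92.0 − 86.7 = 5.3 points, and the median does not move. No general bound follows from the >90% discharge criterion, because footnote a of the Schedule of Activities does not say whether vomitus counts as recovered dose.

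**The case for a change.** The strongest case for a change is that the endpoint is primary and the repair is cheap: a cross-reference, a sentence on emesis, adverse events added to the pre-closure review, and a list of exclusions with reasons. Protocol 9.3 says the SAP will describe how missing, unused and spurious data are handled. SAP Section 7 does this for safety endpoints, concentrations and PK parameters but not for recovery. Diarrhea shows the same tension as vomiting: it is collected for possible radioactivity measurement (Protocol 8.4.2.3) and is also a named ground for exclusion.

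These observations are accurate. SAP 8.2.2 has no pointer, no sentence gives a role or time for adverse-event exclusions, and 8.2.2 does not say whether its listing covers all dosed participants. They show that the plan could be fuller. They do not show that a stated rule or figure is wrong, or that the plan followed as written would mislead. Naming a time would also not blind the judgement, since running recovery governs discharge. A named role and an extra all-dosed summary are matters of preference in a descriptive study.

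**Conclusion.** No change is called for. The population for the primary summary is identifiable from the set's own definition, the emesis and exclusion passages are compatible, and the remaining detail is what analysts settle at the pre-closure review. The study tests no hypothesis and has no decision rule (SAP 4.1 and 4.2), and the listing and individual profiles carry the result.

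In the assumed example, the choice moves the mean by 5.3 points and the median by nothing, and it arises only if the evident set is not used. The conclusion rests on three readings: that 5.1.3 governs 8.2.2, that the total is urine plus feces, and that exclusions are shown under the sponsor's reporting standards, which these documents do not reproduce. If the sponsor later wishes to write any of this down, the opening of Protocol Section 9 lets the SAP carry such detail without a protocol amendment.
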